1.0 Objectives / Specific Aims

The goal of this work is to develop, refine, and pilot test an electronic visit (e-visit) to: 1) deliver smoking cessation treatment to adults at risk for COPD and 2) to improve rates of COPD early detection and accurate diagnosis. We will conduct a pilot RCT (N=100, up to 120 assuming 20% attrition) of the COPD/smoking cessation e-visit as compared to treatment as usual (TAU), with primary objective to provide effect size estimates for a larger RCT. Specific aims are twofold:

Aim 1: Conduct usability testing of the smoking cessation/COPD e-visit with patients (N=5, up to 10 to account for attrition) followed by iterative refinements consistent with participant feedback.

Aim 2: Conduct a pilot, small-scale randomized controlled trial to examine COPD and smoking cessation outcomes associated with the E-Visit as compared to treatment as usual (TAU; i.e., no e-visit). Outcomes will include those related to: e-visit feasibility (i.e., time to complete e-visit, time for provider to review e-visit, % completed e-visits, qualitative feedback), COPD (early diagnosis rates as a function of treatment condition, emergency department visits for respiratory infection), smoking cessation outcomes (self-reported quit attempts/quit duration and biochemically verified cessation via carbon monoxide), and cessation medication utilization.

We hypothesize that participants randomized to the e-visit condition as compared to those randomized to the TAU condition will have higher (numerically, if not statistically significant) rates of COPD early diagnosis, cessation treatment utilization (medications, counseling), and superior cessation-related outcomes.

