2.0 Background

More than 16 million Americans have COPD and millions more suffer from COPD but have not yet been accurately diagnosed or treated¹. Nationwide healthcare costs associated with COPD exceed \$36 billion annually and are projected to reach \$49 billion by 2020¹. COPD is now concentrated within rural communities and those who reside in rural areas as compared to those who reside in large metropolitan areas have both higher COPD incidence (8% vs. 5%) and higher COPD-related death rates (55 per 100,000 vs. 32 per 100,000)². Telehealth strategies to implement evidence-based best practice for COPD may be particularly impactful among rural communities as such treatment modalities can extend the reach of traditional COPD prevention, diagnosis, and treatment strategies.

In light of the significant public health impact of COPD, the National Heart Lung and Blood Institute (NHLBI) issued a COPD National Action Plan in 2017. A key goal within this national action plan is to improve the diagnosis, prevention, treatment, and management of COPD by improving the quality of care delivered across the health care continuum. Informed by this federal national action plan, and with the guidance of HRSA, our team will undertake a 22-month planning and pilot intervention period to identify how telehealth modalities might be optimally leveraged to improve the quality of care and outcomes among patients at risk for COPD. Because COPD is most commonly caused by cigarette smoking, we will focus our planning and intervention period specifically on COPD early detection among cigarette smokers and on leveraging telehealth to extend the reach of evidence-based smoking cessation treatment (i.e., medications and counseling for smoking cessation) for those at risk for COPD. This work will build upon and extend our team's ongoing efforts to develop a smoking cessation electronic visit (e-visit) that can be proactively delivered to all adult MUSC patients who have been identified via the electronic health record as cigarette smokers. E-visits are embedded into the most common electronic health record (EHR) systems (e.g., Epic, Allscripts, and others) and offer a secure platform through which patients can

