4.0 Study Endpoints (if applicable)

Primary outcome variables include:

- Evidence-based cessation treatment utilization will be assessed via participant self-report. At each follow-up assessment, participants in both groups will be queried for: 1) use of a smoking cessation medication since the last assessment, 2) how the medication was obtained (e.g., via the study or another outlet such as MUSC's existing smoking cessation service), and 3) receipt of the 5As from their PCP⁶.
- Cessation-related outcomes will be assessed via participant self-report. Cigarette smoking, use of other tobacco products (e.g., e-cigarettes), and quit attempts/quit duration will be assessed at each follow-up using a timeline followback for the last 6-months at baseline and since prior follow-up for each subsequent assessment^{7,8}.
- COPD diagnosis will be assessed both via established metrics captured via home spirometry and via chart review.

Secondary outcome variables include:

- E-visit acceptability and feasibility will be assessed both by examining the percentage of patients who complete the initial and follow-up e-visits, and by participant self-report during follow-up assessments. Participants will respond to items assessing ease of use, satisfaction, and pros/cons of the e-visit. Analytics data (e.g., amount of time it takes to complete the e-visit, amount of time it takes the provider to review the e-visit) will also be collected as will data on provider fidelity to e-visit recommendations (captured by reviewing within Epic whether the provider administered treatment consistent with e-visit recommendations).

We will also assess:

- Nicotine dependence will be assessed at baseline via the Fagerstrom Test of Nicotine Dependence⁹.
- Motivation to quit and confidence in quitting will be assessed via participant self-report using a modified Contemplation Ladder¹⁰.

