A two-arm pilot RCT (N=100, up to 120 assuming 20% attrition) will test cessation treatment utilization, smoking cessation outcomes, and COPD diagnosis rates as a function of smoking cessation e-visit vs. TAU. Recruitment will primarily occur proactively and remotely via the EMR. We will conduct an automated EMR search via established procedures for all patients treated within MUSC DFM clinics during the past 12 months who: 1) smoke, 2) are ≥ 40 , 3) have MyChart accounts, and 4) do not have COPD on their problem list. **These patients will be sent a MyChart message from a member of their care team inviting them to participate in a research study for cigarette smokers. These messages will only be sent to patients of PCPs who have agreed that their patients may be contacted for the purpose of this study. This invitation will include clear opt out procedures should the patient not wish to be contacted in the future for the purpose of this study. Clinical providers included in the Usability Testing phase of the project will not be asked to directly refer their own patients to the study. However, their patients may still be recruited via the EMR.** After sending these automated e-mail messages via MyChart, the study team may also call, e-mail, and/or text message potential participants to notify them that a message was sent to them via MyChart. Again, such contact will only be made to patients of PCPs who have agreed that their patients may be contacted for the purpose of this study. If interested, participants will complete a screening online via MyChart to determine study eligibility (see above for inclusion criteria). After completing determination of eligibility, if eligible and interested in participating in the study, participants will be scheduled for a time to complete informed consent (see 9.0 Consent Process). After consent is obtained, participants will be randomized 2:1 to receive either the smoking cessation e-visit or TAU. If randomized to the e-visit condition, participants will be sent a link to initiate the e-visit. All e-visit medication recommendations will be reviewed by physicians included on this IRB protocol. Medications will be e-prescribed to a mail order pharmacy (e.g., MUSC's mail order pharmacy) and then mailed to participants, with all costs covered by the study. Note

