For participants randomized to the e-visit condition, the baseline e-visit will include a 5-item questionnaire (the CAPTURE) to assess COPD symptoms. Participants who score ≥ 2 on this measure will be invited to complete home spirometry. These participants will be mailed a home spirometer and will be invited to complete an additional e-visit after receiving the home spirometer at which time they will be instructed regarding how to use the device and will upload a video of themselves completing home spirometry. Participants will also be asked to enter into the e-visit metrics available via the spirometer including FEV1 and peak expiratory flow. These videos will be reviewed by a study attending physician and follow-up care will be provided consistent with best clinical practices. In addition to home spirometry, all patients who screen positive on the CAPTURE during the baseline e-visit will be referred to an in person appointment for spirometry/bronchodilation consistent with best practices. Costs related to in person spirometry testing will be paid for by the study for appointments completed by the time of the 3-month assessment. Although the medical order for spirometry testing may remain active following the 3-month assessment, any testing completed after the date of the 3-month assessment will not be paid for by the study.

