All participants will subsequently be text messaged and/or emailed a REDCap link, accessible via smartphone, tablet, or computer to complete study assessments. These assessments will occur at baseline (following consent), 1-month following study enrollment, and 3-months following study enrollment. Assessments are estimated at 20 minutes each and will be administered remotely via REDCap through our established procedures. Participants will be compensated via electronic gift cards (e.g., Amazon) which will be emailed or texted to participants. Participants will receive \$30 for completion of the baseline assessment questionnaire. After completing each follow-up questionnaire within 72 hours of being emailed the link, participants will be compensated \$30. Participants will be compensated \$30 for each completed carbon monoxide recording. They will be compensated an additional \$100 for completion of all three sets of questionnaires and both carbon monoxide samples. E-visit acceptability and feasibility will be assessed both by examining the percentage of patients who complete the initial and follow-up e-visits, and by participant self-report during follow-up assessments. Participants will respond to items assessing ease of use, satisfaction, and pros/cons of the e-visit. Analytics data (e.g., amount of time it takes to complete the e-visit, amount of time it takes the provider to review the e-visit) will also be collected as will data on provider fidelity to e-visit recommendations (captured by reviewing within Epic

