whether the provider administered treatment consistent with e-visit recommendations). Cigarette smoking, use of other tobacco products (e.g., e-cigarettes), and quit attempts/quit duration will be assessed at each follow-up using a timeline followback for the last 6-months at baseline and since prior follow-up for each subsequent assessment^{7,8}. Nicotine dependence will be assessed at baseline via the Fagerstrom Test of Nicotine Dependence⁹. Participants will report motivation to quit and confidence in quitting using a modified Contemplation Ladder¹⁰. Expired air carbon monoxide will also be captured. Treatment utilization will be assessed via participant self-report. At each follow-up assessment, participants in both groups will be queried for: 1) use of a smoking cessation medication since the last assessment, 2) how the medication was obtained (e.g., via the study or another outlet such as MUSC's existing smoking cessation service), and 3) receipt of the 5As from their PCP⁶. COPD diagnosis will be assessed via participant self-report and via medical records review. At each follow-up time point, participants will be asked whether a clinical provider has given them a COPD diagnosis. Medical records will be reviewed for up to 12-months following completion of the 3-month follow-up survey to identify: 1) whether the participant was referred for in person spirometry, 2) whether the participant attended that appointment, and 3) whether the participant was given a diagnosis of COPD.

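### The COPD chart review is timed from completion of the 3-month survey, with only a maximum length and no rule for survey non-completers, so diagnosis rates may rest on unequal observation

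*Combined protocol and SAP*

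**What the plan says.** Section 4.0 lists COPD diagnosis among the primary outcome variables: "COPD diagnosis will be assessed both via established metrics captured via home spirometry and via chart review". Section 1.0 makes it a between-arm outcome: "COPD (early diagnosis rates as a function of treatment condition".

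Section 10.0 gives the timing of the chart review: "Medical records will be reviewed for up to 12-months following completion of the 3-month follow-up survey to identify" three items, namely referral for in-person spirometry, attendance, and a COPD diagnosis. The same section adds self-report: "At each follow-up time point, participants will be asked whether a clinical provider has given them a COPD diagnosis". Study assessments fall at "baseline (following consent), 1-month following study enrollment, and 3-months following study enrollment".

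The planned size is "A two-arm pilot RCT (N=100, up to 120 assuming 20% attrition"), randomised 2:1. Study payment for in-person spirometry stops at the 3-month assessment: "any testing completed after the date of the 3-month assessment will not be paid for by the study".

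Section 11.0 describes analyses of treatment utilization, quit attempts and e-visit feasibility. It gives no analysis, denominator or follow-up-time adjustment for COPD diagnosis.

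**The concern.** Chart review is the one source for this outcome that could cover both arms completely. Home spirometry is described only for e-visit participants who screen positive on the CAPTURE, so it cannot support an arm comparison. Self-report depends on the follow-up surveys, so its 3-month value is missing whenever that survey is missed. Chart review needs no contact, yet the plan times it from the same survey. Taken literally, the people with no 3-month self-report are also the people with no chart-review window.

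Three things are left open:

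- **Who is reviewed.** There is no anchor date or rule for someone who does not complete the 3-month survey.
- **For how long.** There is a maximum but no minimum and no common closing date.
- **From when.** The literal wording covers time after the survey. The items to be extracted suggest that earlier records are meant too, because the referral follows the baseline e-visit. The text does not say so, and the first three months are when study-paid spirometry takes place.

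The pilot exists to supply effect-size estimates for a larger trial. A proportion diagnosed over an undefined mixture of windows is hard to carry forward. If the mixture differs by arm, the estimated effect is distorted as well.

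**Working it through.** The documents give no COPD rate, power or sample size, so there is no stated figure to reproduce. The checks below size the gap.

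**1. How many participants could lack an anchor date.** Inputs: 120 randomised, 20% attrition, 2:1 allocation (sections 10.0 and 11.0). Assumption: attrition means not completing the 3-month survey.

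- 20% of 120 = 24, or about 16 e-visit and 8 TAU.
- If 100 of the 120 complete, 120 − 100 = 20.

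The exposed number is therefore 20 to 24. The wording puts them at risk of being missed; it does not say that they will be.

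**2. How much window length matters.** The longest observation the text allows is about 3 + 12 = 15 months from enrolment. With no minimum after the survey, it could be as short as about 3 months. Assume a constant hazard and a 15-month risk P (not in the documents). The risk by month t is then 1 − (1 − P)^(t/15).

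| Assumed 15-month risk | By 3 months | By 9 months | By 15 months |
|---|---|---|---|
| 5% | 1.0% | 3.0% | 5.0% |
| 10% | 2.1% | 6.1% | 10.0% |
| 20% | 4.4% | 12.5% | 20.0% |

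The same underlying risk gives very different proportions diagnosed, so a rate without a stated window cannot be interpreted.

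**3. What survey non-completion could do to the arm comparison.** Assume the same true risk p in both arms, non-completers counted as undiagnosed, and non-completion a_E (e-visit) and a_T (TAU). The observed rate is p(1 − a), so the risk ratio is (1 − a_E)/(1 − a_T). The true ratio is 1.00. All the splits are assumed.

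| Non-completion, e-visit / TAU | Risk ratio | Difference at p = 10% |
|---|---|---|
| 20% / 20% | 0.80/0.80 = 1.00 | 8.0% − 8.0% = 0 |
| 15% / 30% | 0.85/0.70 = 1.21 | 8.5% − 7.0% = +1.5 points |
| 10% / 40% | 0.90/0.60 = 1.50 | 9.0% − 6.0% = +3.0 points |
| 25% / 10% | 0.75/0.90 = 0.83 | 7.5% − 9.0% = −1.5 points |

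Equal loss lowers both rates and leaves the ratio alone. Unequal loss creates an apparent effect in either direction. If non-completers were instead dropped from the denominator, the ratio would stay at 1.00 only if completion were unrelated to the risk of diagnosis. The plan does not say which handling applies.

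**4. With one fixed window for everyone randomised.** Survey completion no longer enters the formula. With equal true risk the expected ratio is 1.00 and the expected difference 0, whatever the survey attrition.

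**The case against.** The wording sets an outer limit and does not say that non-completers are skipped. The survey may be meant only to mark the end of the look-back, and the team may intend 12 months for everybody. Payment for follow-up questionnaires is tied to completing them within 72 hours of the link, with a further $100 for completing everything. That should keep anchor dates close together among completers, and the incentives are described identically for both arms. The trial is a pilot, and the tests in section 11.0 are for utilization and quit attempts, so no planned COPD test is invalidated.

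Most of this stands, and it limits the point. Exclusion of non-completers and unequal windows are permitted by the text, not stated. Among completers the spread in start dates is probably small, so the main weaknesses are the non-completers and the open end. None of it supplies the missing rule for a listed primary outcome.

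Two stronger readings are tempting. A reader might infer that the arms' diagnosis rates cannot be compared at all. The documents do not support that: bias needs completion or window length to differ by arm, and balanced loss leaves the ratio at 1.00. A reader might also infer from "our team will undertake a 22-month planning and pilot intervention period" in section 2.0 that late enrollees must have truncated chart review. The documents do not say that records review ends with that period and give no enrolment calendar. Any such shortening would follow enrolment date rather than arm.

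The end of study payment at 3 months is stated openly and is not itself a defect in the window.

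**Conclusion.** The concern holds as a weakness in how a primary outcome is ascertained. The chart review hangs on a post-randomisation act, has only a ceiling on its length, and has no rule for those who do not perform that act. Nothing elsewhere in the document repairs this.

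The exposed group is about 20 to 24 of 120, taking attrition to mean a missed 3-month survey. The possible distortion between arms depends on assumed non-completion splits: none with equal loss, and a risk ratio of 1.21 at 15% against 30%. Differential completion is plausible in this trial, since one arm receives mailed, study-paid medication and follow-up e-visits while the other receives information and advice to contact a PCP. It is a risk, not a documented fact. The plan should be changed because the missing data are avoidable.

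**What to change.** Replace the timing sentence in section 10.0 with a rule of this kind: the medical records of all randomised participants will be reviewed from the date of randomisation to one fixed time after randomisation, whether or not any survey was completed. Choose a length that the last enrolled participant will also reach.

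Add to section 11.0 that COPD diagnosis is reported by arm over that common window, with all randomised participants as the denominator. Records beyond the window may be reported as supplementary.

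The cost is two reworded passages, about 20 to 24 additional charts, and possibly a common window shorter than the present maximum of 12 months after the survey. If the intention is already to review everyone for the full period, the change only records it.

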11.0 Data Analysis and Data Management

Data Analysis

As this is a pilot trial, our primary goal is to estimate an intervention effect size and our secondary goal is to examine the feasibility/acceptability of the e-visit. Precise parameter estimation can be achieved with 25-30 participants per group¹². To estimate an effect size for the smoking cessation e-visit intervention, we will randomize participants 2:1 (active:control), with 67 participants in the active condition and 33 in the control condition. Primary smoking-related outcomes for this trial include cessation treatment utilization (e.g., medication) and quit attempts. Assuming a cessation treatment utilization rate of 48% in the active condition and 11% in the control condition, with 2:1 randomization we will have 95% power to detect an effect. For quit attempts, assuming a quit attempt rate of 24% in the e-visit condition and 6% in the TAU condition, we will have 60% power to detect an effect. Our intent here is not a fully powered trial for cessation, but is rather to collect preliminary data to inform future trials.

Data analysis for the primary objective will focus on descriptive analysis of primary smoking-related outcomes. Descriptive statistics (e.g., frequencies, percentages) will be calculated for the primary smoking-related outcomes (treatment utilization, quit attempts). Because rates of these primary outcomes are expected to be low in control group, we will utilize Fisher's exact tests to compare rates between the e-visit and TAU groups. Secondary exploratory analyses for this primary objective will examine changes in these outcomes over time by treatment condition. We will utilize Generalized Estimating Equations (GEEs) with log link functions, which will allow us to account for correlated repeated measures within study participants. Planned covariates include sex and the main effect of time.

Data analysis for the secondary objective to examine treatment feasibility specifically for the smoking cessation e-visit will focus on descriptive analysis of: 1) % of those initiate the baseline e-visit who complete it, 2) % of those who complete the baseline e-visit who subsequently complete the follow-up e-visit, 3) average time to complete the e-visit (for patients), 4) average time to review the e-visit (for providers), 5) provider fidelity to e-visit recommendations, and 6) participant self-report of e-visit ease of use, interest in using an e-visit again in the future, benefits of using the e-visit, and strengths/challenges of completing the e-visit. The e-visit will be considered feasible and acceptable if: 1) >90% of those who initiate the baseline e-visit complete it, 2) >75% of those who complete the baseline e-visit complete the

follow-up e-visit, 3) providers are faithful to e-visit recommendations >80% of the time, and 4) self-report data indicate participant benefits and ease of use (average score for each ≥ 4 on 5-point scale).

Data Management

Regarding questionnaire data, data will be obtained for research purposes only. All data will be collected, stored, and managed via REDCap, which is a secure, web-based application designed exclusively to support data capture for research studies. REDCap provides secure, web-based flexible applications, including real time validation rules with automated data type and range checks at the time of entry. The underlying database is hosted in a secure data center at MUSC, a secure environment for data systems and servers on campus, and includes redundancy, failover capability, backups and extensive security checks. The system has several layers of protection including user/group account management, "Data Access Groups" which allow data to be entered by multiple groups in one database with segmented user rights for entered data, audit trails for all changes, queries and reports, and Secure Sockets Layer (SSL) encryption. Name and relevant contact information will be obtained to provide compensation and every effort will be made to maintain subject confidentiality, in accordance with HIPAA. All data will be identified only by code numbers (participant IDs). Participant IDs will be linked to participants' names in a password-protected file that is accessible only to the PI and trained research staff.

12.0 Provisions to Monitor the Data to Ensure the Safety of Subjects (if applicable)

This section is based on the recommendations in NIDA's "Guidelines for developing a Data and Safety Monitoring Plan" as well as NCI's "Essential Elements of a Data and Safety Monitoring Plan for Clinical Trials Funded by the National Cancer Institute."

Summary of the Protocol

We will develop and iteratively test a comprehensive e-visit for delivery to smokers treated via primary care. Through an established partnership with MUSC Epic developers, we will develop the e-visit consistent with USPHS best practice guidelines for smoking cessation treatment via primary care. Those who self-report symptoms of COPD will be invited to complete home spirometry. We will then complete a randomized pilot trial of 1) e-visit vs. 2) TAU.

Trial Management

The study will be managed from the Addiction Sciences Division within the Department of Psychiatry and Behavioral Sciences at the Medical University of South Carolina (MUSC). Recruitment, data collection, data management, and treatment provision will be coordinated and centrally managed at our research lab at MUSC and will be implemented within local MUSC clinics.

Data Management and Analysis

Participants will enter data in REDCap, a secure, web-based application designed exclusively to support data capture for research studies. REDCap provides: 1) an intuitive interface for data entry (with data validation); 2) audit trails for tracking data manipulation and export procedures; 3) automated export procedures for seamless data downloads to common statistical packages (SPSS, SAS, Stata, R); 4) procedures for importing data from external sources; and 5) advanced features, such as branching logic and calculated fields. These procedures are effective in minimizing data entry errors (e.g., missing or errant data). The data analysis plan is outlined above.

Quality Assurance

Accuracy and completeness of the data collected will be ensured by weekly review. The REDCap system does not accept outliers, illogical response patterns, etc. The PI and research assistants will have weekly meetings to discuss any qualitative comments received during data collection and any problems in data collection. The PI will examine the database for potential irregularities monthly. Initial data analyses will examine distributions of variable scores and comparability of baseline characteristics across conditions in case analyses need to be adjusted for these. Confidentiality procedures are outlined above.

Regulatory Issues

All serious AEs will be reported to the MUSC Committee on Human Research within 48 hrs. Follow-up of all unexpected and serious AEs will also be reported. All AEs will be reviewed weekly by the PI and yearly by the IRB. Any significant actions taken by the local IRB, and protocol changes will be relayed to the funding agency. We estimate the significant AE rate to be 5% or less. Potential conflicts of interest (COI) will be reported using the SRNT rules for disclosure as well as the rules of MUSC's COI committee.

Trial Safety

The potential risks and benefits and methods to minimize these risks are outlined in the "Risks to Subjects" section. AEs will be tracked and rated as mild, moderate or severe and as related to medication by the participant. We will determine if any AEs result in dropouts, or are serious according to FDA guidelines. The PI ([name]) will serve as the Program Manager for AEs. All unexpected AEs will be monitored while they are active to determine if treatment is needed. Risk profiles for smoking cessation medications that may be prescribed as an outcome of the e-visit are minimal, with the most common side effects being nausea, headache, and dry mouth. All patients will be active MUSC. As such, we expect AEs will be rare. Nonetheless, they will be coded on a weekly basis using the FDA's COSTART rules¹³ and entered into a database. For each weekly study meeting, the research assistant(s) will prepare a summary of all AEs, including their severity, whether they caused a dropout, required treatment and presumed relation to drug intake. The PI will review this at the weekly study meeting (or before if more urgent). Drs. [name] and [name], board-certified Family Medicine physicians, will be available for on-site medical supervision for any issues that cannot be resolved by [name].

Study procedures will follow as much as possible the FDA's Good Clinical Practice Guidelines and our research team has found Spilker's comprehensive text on conducting clinical trials to be useful¹⁴. The research assistants will be instructed not to reveal whether a person is a participant in the study and will report to the PI any outside requests for information about a participant or any breaches in confidentiality. All requests by participant's physicians and other medical providers will be referred directly to the PI.

Data and Safety Monitoring Plan Administration

The PI will be responsible for monitoring the trial. The PI will examine monthly the outcomes database for missing data, unexpected distributions or responses, and outliers. The PI will check weekly the AE database prepared by the research assistant(s) immediately prior to the lab meeting a) to see if any particular COSTART categories are being endorsed more frequently than normal and b) to determine if any side-effect symptom checklist scores are higher than expected. A DSM report will be filed with the IRB and funding agency on a yearly basis, unless greater than expected problems occur. The report will include participant characteristics, retention and disposition of study participants, quality assurance issues and reports of AEs, significant/unexpected AEs and serious AEs. We will report efficacy at the end of the trial.

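### Fisher's exact test for the two primary smoking outcomes is valid but conservative; a prespecified Boschloo test keeps the 5% level and recovers a small, sample-dependent amount of power.

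*Combined protocol and SAP*

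**What the plan says.** Section 11.0 makes treatment utilization and quit attempts the primary smoking-related outcomes. It describes them first and then tests them between arms: "we will utilize Fisher's exact tests to compare rates between the e-visit and TAU groups". The reason given for choosing that test is "Because rates of these primary outcomes are expected to be low in control group".

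The arm sizes are given as "we will randomize participants 2:1 (active:control), with 67 participants in the active condition and 33 in the control condition". Power is quoted for both outcomes:

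- Utilization: "Assuming a cessation treatment utilization rate of 48% in the active condition and 11% in the control condition". The power claimed at these rates is 95%.
- Quit attempts: "assuming a quit attempt rate of 24% in the e-visit condition and 6% in the TAU condition". The power claimed at these rates is 60%.

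Neither alpha nor sidedness is stated. Section 10.0 plans 100 participants, and up to 120 to allow for 20% attrition. Section 11.0 also says that estimating an effect size is the primary goal and that the trial is not meant to be fully powered for cessation.

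**The concern.** Low expected counts are a good reason to prefer an exact test to a large-sample one. They do not by themselves call for a test that conditions on the total number of events. Conditioning makes Fisher's p-value coarse, most of all with small arms and low rates, so the test rejects less often under the null than its nominal level allows. The unused level is lost power.

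The design fixes the arm sizes but not the total number of quit attempters or medication users. An exact test that conditions only on the arm sizes also guarantees 5% and can use more of it. What is at stake is some power for quit attempts, the weaker of the two primary outcomes at 60% by the plan's own figure.

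**Working it through.** **Inputs.** Arms of 67 and 33; quit attempts 24% v 6%; utilization 48% v 11% (all section 11.0). Two-sided 0.05 is an assumption. The common (pooled) rates are:

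- Quit attempts: (67 × 0.24 + 33 × 0.06)/100 = (16.08 + 1.98)/100 = 18.1%.
- Utilization: (67 × 0.48 + 33 × 0.11)/100 = (32.16 + 3.63)/100 = 35.8%.

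**Method.** Enumerate all 68 × 34 outcomes (x, y). With R the set of tables that a test rejects,

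P(reject) = Σ over (x, y) in R of Bin(x; 67, p₁) × Bin(y; 33, p₂).

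Setting p₁ = p₂ gives the true size; using the plan's rates gives power.

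**1. The plan's own power figures.** For Fisher, R is the set of tables with two-sided p ≤ 0.05.

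- Quit attempts: 60.1%, which reproduces the stated 60%. Hand check with the pooled normal formula: null SE = √(0.1806 × 0.8194 × (1/67 + 1/33)) = 0.0818; alternative SE = √(0.24 × 0.76/67 + 0.06 × 0.94/33) = 0.0666; (0.18 − 1.96 × 0.0818)/0.0666 ≈ 0.295, so power is about 61.6%.
- Utilization: 97.7%, against the stated 95%, so the plan understates this one. Fisher at two-sided 0.025 gives 95.0%, but then quit attempts fall to 45.8%. No single variant tried reproduces both figures.

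**2. True size of Fisher's test at 67/33.**

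| Outcome | TAU rate | Pooled rate | E-visit rate |
|---|---|---|---|
| Quit attempts | 2.8% (at 6%) | 3.7% (at 18.1%) | 3.7% (at 24%) |
| Utilization | 3.2% (at 11%) | 3.9% (at 35.8%) | 3.4% (at 48%) |

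The maximum over all common rates is 3.9%.

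**3. Boschloo's test.** It orders tables by the two-sided Fisher p-value and rejects when that value is ≤ c, where c is the largest cut-off whose size is ≤ 5% at every common rate. Fisher's own cut-off of 0.05 already meets that condition, so c ≥ 0.05. Every table that Fisher rejects is therefore rejected, and power cannot be lower. At 53/27, for example, c is 0.0584. The maximum size at 67/33 is 4.8%.

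Power for quit attempts (24% v 6%):

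| Analysed, e-visit/TAU | Fisher | Boschloo | Gain (points) |
|---|---|---|---|
| 53/27 | 43.3% | 51.8% | 8.5 |
| 60/30 | 53.2% | 59.8% | 6.6 |
| 64/32 | 58.3% | 58.3% | 0 |
| 67/33 | 60.1% | 61.8% | 1.7 |
| 80/40 | 70.1% | 72.9% | 2.8 |

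The 80/40 row is 120 analysed in full. The 64/32 row is 120 less 20% (120 × 0.8 = 96). The 53/27 row is 100 less 20%.

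Power for utilization rises from 97.7% to 98.0% at 67/33 (about 0.3 points) and from 93.2% to 94.8% at 53/27.

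**4. The two-sided definition matters.** A version built from two one-sided Boschloo tests at 2.5% has size 2.4% at a 6% common rate, below Fisher's 2.8%. It must therefore leave out some tables that Fisher rejects, so the guarantee in step 3 does not apply to it.

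**5. Barnard's test on the pooled score statistic.** It reaches 63.6% at 67/33 (maximum size 4.9%), but it is the weaker candidate:

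- It is not always ahead of Boschloo: 56.2% v 59.8% at 60/30, and 65.7% v 67.1% at 70/35.
- At 64/32 it fails to reject two tables that Fisher rejects.
- At 67/33 it calls 0/67 v 2/33 significant. Fisher's p there is C(33,2)/C(100,2) = 528/4950 = 0.107. The pooled score is (2/33)/√(0.02 × 0.98 × (1/67 + 1/33)) = 0.0606/0.0298 = 2.04. That would be a finding in favour of TAU on two events.

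**The case against.** The strongest reply is that nothing is broken. Fisher's test controls the level, and the quit-attempt power was evidently worked out for it. The trial is a pilot: section 11.0 puts estimation and description first, section 1.0 expects differences that may be only numerical, and the success thresholds in section 11.0 are feasibility percentages that use no p-value. If the null is that the e-visit changes no participant's outcome and arm sizes are fixed, total events are fixed too and Fisher's test is the randomization test. Conditioning is then a defensible choice. The gain is also erratic: at 64/32, which is what 120 recruits less 20% would leave, Boschloo adds nothing for quit attempts.

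All of this stands, and it sets the weight of the point. It does not remove the gain. The plan commits to a between-arm test on both outcomes and quotes power for each, and its stated reason supports an exact test without favouring Fisher over Boschloo.

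A reader might infer that Fisher's test pulls quit-attempt power below the stated 60%. It does not; 60% is the power with Fisher. A reader might also infer that the full 5% can be recovered. At a 6% common rate Boschloo still uses only about 3.0%, against Fisher's 2.8%.

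**Conclusion.** The point holds as a minor efficiency improvement. Assuming two-sided 0.05 at 67/33, Fisher's true size is 2.8% to 3.9% at the plan's rates. Boschloo's test keeps the 5% level and never has less power. For quit attempts the gain over the sample sizes checked runs from 0 to 8.5 points and is 1.7 points at the planned size. As a yardstick, two more participants (68/34) would take Fisher itself to 62.3%. For utilization at the planned size the gain is negligible.

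The documents do not support the stronger readings that the plan's analysis is invalid, that its quit-attempt power is overstated, that both primary comparisons lose material power at the planned size, or that Barnard's test is the better replacement.

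The figures rest on the assumed alpha and sidedness, on the plan's event rates, and on the numbers analysed in each arm, which attrition leaves uncertain.

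**What to change.** In section 11.0, replace the Fisher sentence with one along these lines, before any outcome is compared by arm: *Treatment utilization and quit attempts will each be compared between arms with Boschloo's exact unconditional test at a two-sided 5% level, ordering tables by the two-sided Fisher p-value and maximising over the common rate, using [software and version].*

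The ordering statistic must be named, because packages can define the two-sided test differently and only this form is sure to contain Fisher's rejections. Barnard's pooled-score test should not be the first choice.

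The cost is one sentence, with no added participants, visits or data. The drawbacks are a test that readers know less well and little recovery of the level when rates are as low as 6%. If the team prefers to keep Fisher's test, that is acceptable, but section 11.0 should still state alpha and sidedness.
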